8.3.5. Survival Follow-up

Survival follow-up includes progression-free survival, PFS by clinical judgment and overall survival.

All subjects will be followed for tumor progression (CT/MRI or clinical judgment) and overall survival (OS) time or the date of withdrawal. Subjects who remain alive after study completion will have their OS time censored on the last date known to be alive.

8.4. Data Sources

This NI study data will be recorded by a physician/nurse in the medical records, through subject interview, and in the electronic Case Report Form (CRF).

8.5. Study Size

The sample size for this study is not based on statistical considerations. Since the study is designed to observe the clinically relevant outcomes in patients treated in real world and based on discussion with potential investigators that there are totally about 20 patients per year in their hospitals, it was decided to have a sample size of approximately 100 patients who would be enrolled over five years.

8.6. Data Management

Datalabs is the Electronic Data Collection (EDC) system for the study. Discrepancy management is used to identify and manage potential problems with study data. Datalabs generates discrepancies during data entry and discrepancy management whenever there is a missing or inconsistency between the data entered and the validation specifications. Datalabs identifies a problem and creates a discrepancy entry in the database.

The investigator is responsible to collect study data, including the eCRF data, laboratory data, via the EDC system in a timely manner and to ensure the integrity, accuracy, and completeness of the data.

The investigator should keep accurate records of: identity of all subjects (sufficient information to link the patients to the corresponding study data), serious adverse event forms, all related source documentation, details of treatment disposition, as well as relevant correspondence details (eg, letters, emails, meeting minutes, telephone call reports). The investigator record retention period should comply with the local regulations, or as specified in the Clinical Study Agreement, whichever is longer.

If the investigator becomes unable for any reason to continue to retain study records for the required period (eg, retirement, relocation), Pfizer should be notified. The study records must be transferred to a designee acceptable to Pfizer, such as another investigator, another institution, or to an independent third party arranged by Pfizer. The investigator must obtain Pfizer's written permission before disposing of any records, even if retention requirements have been met.

8.7. Data Analysis

Detailed methodology for summary and statistical analyses of data collected in this study will be documented in a Statistical Analysis Plan (SAP), which will be dated, filed and maintained by the sponsor. The SAP may modify the plans outlined in the protocol; any major modifications of primary endpoint definitions or their analyses would be reflected in a protocol amendment.

The results of this study will be presented using descriptive statistics. The primary analysis will be performed on all subjects who receive at least one dose of sunitinib.

Data will be collected in a standard format electronic CRF as described in the Study Procedures (see 8.3 Variables).

All analyses will be performed on all subjects who receive at least one dose of Sunitinib.

Primary safety outcomes include the frequency of adverse events and serious adverse events. Adverse events of particular interest are as follows:

- Infections and infestations.
- Cardiac and vascular.
- Skin and subcutaneous tissue:
 - The most common skin and subcutaneous tissue related adverse events of interest are rash (includes erythematous, macular, or scaly rash), hand foot syndrome (HFS) or palmo plantar erythrodysesthesia (PPE), dry skin and skin discoloration.
- Gastrointestinal.
- Psychiatric and nervous system.

- Musculoskeletal.
- Thyroid function.
- General disorders.
- Others.
- laboratory abnormalities:
 - Haematologic: hemoglobin, platelet count, white blood cell count, neutrophile granulocyte count.
 - Non Haematologic: total bilirubin, ALT (Alanine Transaminase), AST (Aspartate Transaminase), alkaline phosphatase, GGT (Gamma-Glutamyl Transferase), total protein, albumin, BUN (Blood Urea Nitrogen), creatinine, uric acid, glucose, hypocalcemia, hyponatremia, hypophosphatemia, hypokalemia.

Secondary efficacy endpoints are the progression-free survival time, progression-free survival by clinical judgment, overall survival time and 5-year survival rate.

Progression-Free Survival is defined as the time from the start of sunitinib treatment to first documentation of objective tumor progression or to death due to any cause, whichever occurs first. PFS data will be censored on the date of the last tumor assessment on study for subjects who do not have objective tumor progression and who do not die while on study.

Default start date is date of first treatment, if this date is not available, date of enrollment will be used.

Progression-free survival by clinical judgment is defined as the time from the start of sunitinib treatment to first document of objective tumor progression, or first time tumor progression diagnosed by investigator based on clinical judgment, or death due to any cause, whichever occurs first. PFS by clinical judgment data will be censored on the date of the last tumor assessment on study for subjects who do not have tumor progression (objective or based on clinical judgment) and who do not die while on study.

Subjects lacking an evaluation of tumor response after “start of sunitinib treatment will have their PFS and PFS by clinical judgment time censored on the date of “start of sunitinib treatment. Additionally, subjects who start a new anti-cancer therapy prior to Progressive Disease (PD) will be censored at the date of the last tumor assessment prior to the start of the new therapy.

Overall Survival (OS) is defined as the time from the start of sunitinib treatment to documentation of death due to any cause. Subjects who withdraw from study will have their OS time censored on the date of withdrawal, and subjects who remain alive after study completion will have their OS time censored on the last date known to be alive.

5-year survival rate is defined as the percentage of patients who stay alive till after 5 years from the start of sunitinib treatment.

For secondary efficacy time-to-event endpoints (PFS, PFS by clinical judgment and OS), the Kaplan-Meier method will be used to obtain the estimates of median event-free time. Confidence intervals for the 25th, 50th and 75th percentiles of the event-free time will be reported based on the sign test (produced with “PROC LIFETEST” in SAS).

For 5-year survival rate, the estimate and 95% confidence interval will be calculated from the Greenwood method (produced with “PROC LIFETEST” in SAS).

Safety data will be tabulated and listed according to Pfizer’s standard reporting algorithms. Medical Dictionary for Regulatory Activities (MedDRA) and WHO drug dictionary will be used.

Additional details of the analysis will be provided in the statistical analysis plan and/or the clinical study report. This information may include details of missing and, if applicable, unused and spurious data. Deviations from the statistical plan will be reported in the clinical study report.

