8.2.5. Inclusion criteria

Patients must meet all of the following inclusion criteria to be eligible for inclusion in the study:

Patient's eligibility should be reviewed and documented by an appropriately qualified member of the investigator's study team before subjects are included in the study.

1. Evidence of a personally signed and dated informed consent document indicating that the subject (or a legally acceptable representative) has been informed of all pertinent aspects of the study.
2. Subjects who will accept sunitinib therapy, or subjects who have already taken sunitinib within the past 6 months (26 weeks) and will continue sunitinib therapy, and are willing to follow up visits within current clinical practice.
3. Histologically or cytologically proven diagnosis of well-differentiated pancreatic neuroendocrine tumors (according to WHO 2000 classification).²
4. Unresectable (as assessed by the investigator) or metastatic disease documented on a scan.
5. Age ≥ 18 years.

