10.1.1. Reporting Period

For each patient, the safety event reporting period begins at the time of the patient's first dose of Sunitinib or the time of the patient's informed consent if s/he is already exposed to Sunitinib, and lasts through the end of the observation period of the study, which must include at least 28 calendar days following the last administration of a drug under study; a report must be submitted to Pfizer Safety (or its designated representative) for any of the types of safety events listed in the table above occurring during this period. If a patient was administered a drug under study on the last day of the observation period, then the reporting period should be extended for 28 calendar days following the end of observation. Most often, the date of informed consent is the same as the date of enrollment. In some situations, there may be a lag between the dates of informed consent and enrollment. In these instances, if a patient provides informed consent but is never enrolled in the study (eg, patient changes his/her mind about participation, failed screening criteria), the reporting period ends on the date of the decision to not enroll the patient.

If the investigator becomes aware of a SAE occurring at any time after completion of the study and s/he considers the SAE to be related to sunitinib, the SAE also must be reported to Pfizer Safety.

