5.3. Safety Analysis Set

The safety population will be defined as all enrolled patients who take at least one dose of the study drug; all summaries of safety will be reported within the safety analysis set. The safety analysis set is the same as full analysis set in this study.

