8. STATISTICAL METHODOLOGY AND STATISTICAL ANALYSES

8.1. Statistical Methods

This section gives a general overview of the statistical methodology for the efficacy and safety endpoints.

The results of this study will be presented using descriptive statistics.

All analyses will be performed on (a) all FAS subjects who receive at least one dose of Sunitinib, (b) FAS subjects who have not taken sunitinib within the past 6 months (26 weeks) and will accept sunitinib therapy, and (c) FAS subjects who have already taken sunitinib within the past 6 months (26 weeks) and will continue sunitinib therapy.

All analyses will be based on the data collected during the study.

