8.2. Statistical Analyses

8.2.1. Analysis of Primary Safety Endpoints

Safety endpoints will be summarized for the safety analysis set.

Safety data, such as AEs, vital signs, ECOG status, laboratory data, physical examination etc., will be tabulated and listed according to Pfizer’s standard reporting algorithms. Medical Dictionary for Regulatory Activities (MedDRA) and WHO drug dictionary will be used. The severity of all AEs will be coded using NCI CTCAE Version 4.0.

For the adverse events of particular interest, 95% CI will be presented using the exact method (Clopper-Pearson interval).

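### The primary adverse event frequencies pool new starters with prior users admitted only if they continue sunitinib, and the plan does not say which group supports conclusions about risk from the start of treatment

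*Protocol*

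**What the plan says.** Inclusion criterion 2 (Protocol 8.2.5) has two routes. One is for patients about to start sunitinib. The other, added by Amendment 1 because recruitment was difficult in a rare disease, is for "subjects who have already taken sunitinib within the past 6 months (26 weeks) and will continue sunitinib therapy".

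The main safety result combines both routes. Protocol 8.7 says "The primary analysis will be performed on all subjects who receive at least one dose of sunitinib" and "Primary safety outcomes include the frequency of adverse events and serious adverse events". SAP 5.3 agrees: "The safety population will be defined as all enrolled patients who take at least one dose of the study drug", and it equates this set with the Full Analysis Set (FAS).

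SAP 8.1 then asks for three versions of everything. It begins "All analyses will be performed on (a) all FAS subjects who receive at least one dose of Sunitinib"; the second group is listed as "b) FAS subjects who have not taken sunitinib within the past 6 months (26 weeks) and will accept sunitinib therapy"; the third, (c), is the prior users. None of the three is named as the one that answers the primary objective. SAP 8.2.1 adds exact (Clopper-Pearson) 95% intervals for the adverse events of particular interest, whose categories are listed in SAP 6.2.

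Two further places matter. Under Protocol 10.1.1, safety reporting for a prior user starts at "the time of the patient's informed consent if s/he is already exposed to Sunitinib". Protocol 8.9, on limitations, mentions only variation in clinical judgment and practice.

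**The concern.** Take two patients who start sunitinib on the same day, before either has enrolled. One stops at week 6 for toxicity, or dies. The other tolerates treatment and is approached at week 20. Only the second can enter. Prior users are therefore a group that has already passed a tolerance test, while patients enrolled before dosing have not.

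This is separate from the question of when adverse event counting begins. Even if every event since first dose were retrieved for the prior users who enrol, the early stoppers would still be absent, because they never enter the dataset.

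At stake is the primary objective, the safety profile, in a study run to meet a post-marketing commitment. The events exposed to this selection are fatal and treatment-ending ones. A frequency from a partly selected set does not describe the risk facing a patient about to start, and an exact interval reflects sampling error only, so it does not repair selection.

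**Working it through.** **Inputs from the documents.** Protocol 8.5 gives about 20 patients a year over five years: 20 × 5 = 100, which reproduces the stated size. That size has no statistical basis and serves here only as N = 100. The documents do not give the share of prior users (f) or the frequency of early treatment-ending events among starters (q). Both are assumed below and shown as ranges.

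**General relation.** Let r_b be the expected frequency in patients enrolled before dosing and r_c that in prior users.

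- Pooled frequency = (1 − f) × r_b + f × r_c
- Relative understatement = f × (1 − r_c / r_b)

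Everything turns on r_c / r_b.

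**Lower end: constant hazard.** With hazard h per week, a prior user still on treatment at consent has probability 1 − exp(−hT) of an event in the next T weeks. A new starter has the same probability over T weeks. For equal follow-up from consent, r_c = r_b and the understatement is 0, whatever f is.

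**Upper end: all such events precede entry.** Then r_c = 0, the pooled frequency is q × (1 − f), and the relative understatement equals f.

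| True q | f = 20% | f = 40% | f = 60% |
|---|---|---|---|
| 5% | 4% | 3% | 2% |
| 10% | 8% | 6% | 4% |
| 20% | 16% | 12% | 8% |

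**In between: unequal susceptibility.** Assume 20% of starters are susceptible and half of these have the event early and stop. Of the susceptible who remain, 60% have it later; of the non-susceptible, 10% have it later.

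- New starters: 0.2 × (0.5 + 0.5 × 0.6) + 0.8 × 0.1 = 24.0%
- Susceptible share among continuers: 0.1 / 0.9 = 11.1%
- Prior users: 0.111 × 0.6 + 0.889 × 0.1 = 15.6%
- Pooled at f = 20%, 40%, 60%: 22.3%, 20.6%, 18.9%
- Relative understatement at f = 40%: 0.4 × (1 − 15.6 / 24.0) = 14%

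**Intervals.** Clopper-Pearson 95%, q = 10%, at the upper-end case:

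| f | Pooled set (a) | Group (b) only |
|---|---|---|
| 20% | 8/100: 3.5% to 15.2% | 8/80: 4.4% to 18.8% |
| 40% | 6/100: 2.2% to 12.6% | 6/60: 3.8% to 20.5% |
| 60% | 4/100: 1.1% to 9.9% | 4/40: 2.8% to 23.7% |

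At f = 60% the pooled interval lies just below the true 10%. The group (b) estimate is centred on 10% throughout, with a wider interval.

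**The case against.** The strongest reply is that the plan already handles most of this. SAP 8.1 requires every analysis in (a), (b) and (c), so the new-starter frequencies will sit beside the pooled ones. The study is descriptive, with no hypotheses and no decision rules (SAP 4.1, 4.2), so no formal decision depends on which table is called primary. The regulator asked for data from every patient, and prior users were admitted because the disease is rare. All of this stands. It means that no analysis is missing, and that the pooled result should still be reported. It does not settle which of three possibly different frequencies supports the conclusion, and protocol 8.7 currently points to the pooled one.

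The direction is also conditional. If earlier events are retrieved for prior users, their longer exposure could raise crude frequencies of late or cumulative events. This stands too, so a general statement that the pooled set is biased downward would be wrong.

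Group (b) is not strictly a first-use group. Its definition excludes only exposure in the past 26 weeks, so a patient treated longer ago could be in it. The fix must describe it that way.

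Timing deserves care. The three-group sentence entered the SAP in June 2016, and the first interim report, planned for March 2017, was to include all final analyses. A change of emphasis after the May 2018 SAP would come after group-level results were due. The amendment should give its design rationale and say so.

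**Conclusion.** The concern holds, conditionally. The entry rule excludes early failures among those who began before enrolment, and the pooled set carries the primary frequencies. For treatment-ending or fatal events this understates risk from the start of treatment if such toxicity is front-loaded or susceptibility varies. The relative size lies between 0 and f, and the documents do not allow it to be narrowed. Patients enrolled before dosing contribute their early events in full.

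Two stronger readings are tempting and are not supported.

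- **A fixed understatement of about 11% to 24%.** A reader might take a constant hazard, spread prior users' entry over 0 to 26 weeks and stop the clock at week 26 from first dose. The prior-user rate is then 1 − 26h(1 − p)/p, with 26h = −ln(1 − p). For p = 20% it is 10.7%, and the pooled rate is 17.7% at f = 25% and 15.4% at f = 50%. The arithmetic is right, but the gap comes from truncating prior users' time at risk. No document defines a week-26 incidence, and under the same hazard with follow-up from consent the gap is zero.
- **Off-centre intervals for the adverse events of particular interest.** Those intervals cover broad categories such as infections, skin and thyroid. The calculations above concern treatment-ending events, and no shift is shown for tolerable events or for these categories as a whole.

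**What to change.** - In protocol 8.7 and SAP 8.2.1, state that conclusions on adverse event and serious adverse event frequency from the start of treatment, with their Clopper-Pearson intervals, rest on group (b), described as patients with no sunitinib in the 26 weeks before enrolment.
- Present (c) and the pooled set (a) alongside, with (a) labelled as including patients selected for continuing treatment.
- Add this selection to the limitations in protocol 8.9, and report the number of prior users so that f is known.

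The cost is precision: assuming 40% prior users and a 10% rate, group (b) gives 6/60, with an interval of 3.8% to 20.5%. The change also needs a protocol wording amendment, since protocol 8.7 routes major changes to the primary analysis through one. No new data or outputs are needed, because SAP 8.1 already plans all three sets of tables.

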8.8. Quality Control

During study conduct, Clinical Research Associates (CRAs) or study manager will conduct periodic monitoring visits to ensure that the protocol and Good Clinical Practices (GCPs) are being followed. The monitors may review source documents to confirm that the data recorded on CRFs is accurate. The investigator and institution will allow CRAs or study manager monitors and appropriate regulatory authorities direct access to source documents to perform this verification.

It is important that the investigator(s) and their relevant personnel are available during the monitoring visits and possible audits or inspections and that sufficient time is devoted to the process.

8.9. Limitations of the Research Methods

Due to the real world nature of this study, heterogeneity of clinical judgment and clinical practice may exist which may include but is not limited to the following: timing of imaging/laboratory testing, different measurement techniques/standards for judging tumor change.

8.10. Other Aspects

Not applicable.

9. PROTECTION OF HUMAN SUBJECTS

9.1. Patient Information and Consent

All parties will ensure protection of patient personal data and will not include patient names on any sponsor forms, reports, publications, or in any other disclosures, except where

required by laws. In case of data transfer, Pfizer will maintain high standards of confidentiality and protection of patient personal data.

The informed consent form must be in compliance with local regulatory requirements and legal requirements.

The informed consent form used in this study, and any changes made during the course of the study, must be prospectively approved by both the IRB/IEC and Pfizer before use.

The investigator must ensure that each study patient, or his/her legally acceptable representative, is fully informed about the nature and objectives of the study and possible risks associated with participation. The investigator, or a person designated by the investigator, will obtain written informed consent from each patient or the patient's legally acceptable representative before any study-specific activity is performed. The investigator will retain the original of each patient's signed consent form.

9.2. Patient Withdrawal

Patients may withdraw from the study at any time at their own request or they may be withdrawn at any time at the discretion of the investigator or sponsor for safety, behavioral, or administrative reasons. In any circumstance, every effort should be made to document subject outcome, if possible. The investigator should inquire about the reason for withdrawal and follow-up with the subject regarding any unresolved adverse events.

When subjects are permanently withdrawn from treatment, the primary reason for discontinuation must be provided. Reasons for discontinuation include:

- Death due to any cause.
- Unacceptable toxicity.
- Withdrawal of subject consent.
- Other reason.

If the patient withdraws from the study, and also withdraws consent for disclosure of future information, no further evaluations should be performed, and no additional data should be collected. The sponsor may retain and continue to use any data collected before such withdrawal of consent.

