8. RESEARCH METHODS

8.1. Study Design

This study is a multi-center, prospective, Non-interventional (NI) Study evaluating the safety and efficacy of CFDA approved sunitinib in Chinese patients with progressive, unresectable, advanced or metastatic well-differentiated, pancreatic neuroendocrine tumors.

Approximately 100 adults with progressive advanced or metastatic well-differentiated unresectable pancreatic neuroendocrine tumors in China hospitals are the target population. Receipt of any previous systemic therapies is not an exclusion criteria. Each subject will be followed up overall survival (OS) time or the date of withdrawal and subjects who remain alive after study completion will have their OS time censored on the last date known to be alive. The dosage of sunitinib is based on individual safety and tolerability in daily clinical practice. Subjects will be treated until disease progress, unacceptable toxicity, withdrawal of subject consent, other withdrawal criteria are met. Subjects with evidence of disease progression may continue on treatment if judged to have clinical benefit. After discontinuation of treatment and mandated 28 day follow-up, subjects will be followed to collect information on further antineoplastic therapy and the time to death as appropriate or until the subjects withdraw their informed consents during the study period. Subjects who

remain alive after study completion will have their OS time censored on the last date known to be alive.

The NI study will capture observations that will be used for evaluating the safety profile of sunitinib, including: subject demographics, medical history and medications. Safety assessments, treatment data and any other laboratory examination results, which were done according to routine clinical practice, will be collected at all visits.

Concomitant medication will be recorded in the case report form.

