8.2.2. Duration of Subject Participation

The frequency of the NI study visits may be conducted following the local medical advice and it is usually once in 1 or 2 months. In the post-treatment follow-up visit, in the event a subject is unable to return to the clinic for the visit, telephone contact with the subject to assess adverse events and concomitant medications and treatments is expected and is to be conducted at least 28 calendar (+10 days). If the subject withdraws from the study, and also withdraws consent for disclosure of future information, no further evaluations should be performed, and no additional data should be collected. The sponsor may retain and continue to use any data collected before such withdrawal of consent. All subjects who don't withdraw from the study will be followed for survival status (if permitted).

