8.2.4. Definitions of Subject Withdrawal

Subject may be withdrawn from treatment in the case of:

- Subject lost to follow-up.
- Withdrawal of subject consent (cessation of follow-up).

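### Patients withdrawn from the study by the investigator or sponsor fall outside planned survival follow-up and are censored for OS and 5-year survival at that date, and the withdrawal sections contradict one another

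*Protocol*

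**What the plan says.** Protocol 9.2 opens with withdrawal from the study. A patient may choose to leave. Beyond that, "they may be withdrawn at any time at the discretion of the investigator or sponsor for safety, behavioral, or administrative reasons". It continues: "In any circumstance, every effort should be made to document subject outcome, if possible". A further sentence covers the reason for leaving and events still open at that point: "The investigator should inquire about the reason for withdrawal and follow-up with the subject regarding any unresolved adverse events". A separate paragraph deals with treatment: "When subjects are permanently withdrawn from treatment, the primary reason for discontinuation must be provided". Unacceptable toxicity is listed there, among the reasons for stopping treatment. The only ban on further data is narrow: "If the patient withdraws from the study, and also withdraws consent for disclosure of future information, no further evaluations should be performed".

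The other sections define follow-up differently:

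- **Protocol 8.1** contains two rules. One follows each subject for OS or to the date of withdrawal. The other says "After discontinuation of treatment and mandated 28 day follow-up, subjects will be followed to collect information on further antineoplastic therapy and the time to death"; the only earlier end point it names is the patient's withdrawal of consent.
- **Protocol 8.2.2** says that subjects who have not withdrawn from the study "will be followed for survival status (if permitted").
- **Protocol 8.2.4** is headed as a definition of subject withdrawal but begins "Subject may be withdrawn from treatment in the case of". It lists only loss to follow-up and withdrawal of consent.
- **Protocol 8.3.5** follows progression and OS up to the withdrawal date. The abstract and SAP 2.1 repeat this.
- **Protocol 8.7 and SAP 6.1.3** censor OS at the date of withdrawal for subjects who withdraw from the study, with no distinction by reason. SAP 6.1.4 applies the same censoring to 5-year survival.

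**The concern.** The study observes routine care. It sets no visits (8.3) and leaves dosage to daily practice (8.1). Removing a patient from it does not in itself change treatment; its direct effect is on data. The regulator's commitment, quoted in section 6, asks for safety and efficacy data from every patient and survival data for at least 5 years. A route by which the investigator or sponsor can end planned survival follow-up, without the patient asking to leave, works against that commitment.

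One of the three grounds is safety, which may be related to prognosis. Kaplan-Meier estimation assumes that a censored patient has the same future risk as those still followed. If patients withdrawn at discretion die sooner, OS and 5-year survival look better than they are. The analysis plan does not examine this: the only sensitivity analysis in SAP 8.2.2 excludes major protocol deviations, and Protocol 8.9 does not list it as a limitation.

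**Working it through.** **Step 1. Follow each kind of exit through the text.**

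| Exit | Planned survival follow-up | Use in OS |
|---|---|---|
| Stops sunitinib, stays in study | Yes, to death or consent withdrawal (8.1) | Death counts; otherwise censored when last known alive |
| Withdrawn from study by investigator or sponsor (9.2) | Outside 8.2.2; ends at withdrawal under 8.3.5; best-effort outcome only under 9.2 | Censored at withdrawal (8.7, SAP 6.1.3) |
| Withdraws and also refuses further disclosure | None allowed (8.2.2, 9.2) | Censored at withdrawal |

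The second row is the problem. Section 9.2 asks sites to find out the outcome, yet a death found that way falls after the censoring date and would not count. Section 8.2.4 does not recognise this exit at all, and it uses treatment wording for two events that end observation.

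**Step 2. Illustrate the size.** The plan gives no withdrawal rate, no expected survival and no figure of its own to reproduce. The following are assumptions, not document figures:

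- exponential survival, with 5-year survival S in patients not withdrawn of 30%, 50% or 70%;
- a share w of those alive at 6 months is withdrawn then and censored;
- from then on their death hazard is HR times that of the others.

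Six months is one tenth of 5 years, so survival to 6 months is S^0.1, and survival from there to 5 years is S^0.9 in those who stay and S^(0.9·HR) in those withdrawn.

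- Kaplan-Meier estimates S.
- True 5-year survival = S^0.1 × [(1 − w) × S^0.9 + w × S^(0.9·HR)].
- Bias = w × S^0.1 × [S^0.9 − S^(0.9·HR)].

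Example with S = 0.5, w = 0.10, HR = 2: 0.5^0.1 = 0.933, 0.5^0.9 = 0.536 and 0.5^1.8 = 0.287. The bias is 0.10 × 0.933 × (0.536 − 0.287) = 0.023, or 2.3 points.

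Upward bias in percentage points:

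| w | HR 1, S = 50% | HR 1.5, S = 50% | HR 2, S = 50% | HR 3, S = 50% | Range, S 30–70%, HR 1.5–3 |
|---|---|---|---|---|---|
| 2% | 0 | 0.27 | 0.46 | 0.71 | 0.2–0.7 |
| 5% | 0 | 0.67 | 1.16 | 1.78 | 0.5–1.8 |
| 10% | 0 | 1.34 | 2.32 | 3.56 | 1.0–3.6 |
| 20% | 0 | 2.68 | 4.64 | 7.13 | 2.1–7.1 |

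**Step 3. Compare with sampling error.** With 100 patients, 50% survival and no censoring, the 95% half-width is 1.96 × √(0.5 × 0.5 / 100) = 0.098, about 10 points. The bias is smaller than this in every cell, but the confidence interval does not reflect it.

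**The case against.** A reader might infer that 9.2 ends survival follow-up in patients with toxicity. The documents do not support that. Unacceptable toxicity appears in 9.2 as a reason for stopping treatment, and 8.1 keeps following patients who stop treatment. Section 9.2 does not itself forbid data after a discretionary withdrawal; its ban needs withdrawal of consent for disclosure.

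A reader might also infer that later serious adverse events are cut off. That is too strong as well. Section 8.3.4 assesses adverse events within 28 (+10) days after end of treatment or study withdrawal, and continues to follow all serious and possibly related events after withdrawal. Section 10.1.1 requires reporting for at least 28 days after the last dose, and reporting of related serious events learned of after study completion. Much of the primary safety information is therefore protected. None of this supplies long-term vital status.

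Two further objections have weight. First, the wording in 8.2.2 and 8.7 is in the active voice, and in 8.2.2 it directly follows sentences on the subject's own withdrawal, so applying it to patients removed by others is an interpretation. That is fair, but no text says otherwise, and 8.3.5 uses the date of withdrawal without qualification. A site or programmer could reasonably read it either way, which is itself the defect. Second, withdrawal from observation at discretion may be rare, and removal on administrative grounds need not be related to prognosis. That also stands, and it limits the likely size.

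**Conclusion.** The point holds in a limited form. The plan allows a patient to be withdrawn from the study without asking to leave, plans no survival follow-up after that, and censors OS and 5-year survival at that date even if a later death is known. Sections 8.1, 8.2.2, 8.2.4, 8.3.5, 8.7 and 9.2 do not agree on who is followed and until when. It concerns only patients withdrawn from the study at discretion.

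The censoring may be informative, and the bias is upward if these patients have a higher risk of death. Its size cannot be known from the documents. The illustration rests on exponential survival, withdrawal at 6 months and assumed hazard ratios; a lower risk in those withdrawn would reverse the sign. At plausibly low withdrawal rates the effect is modest beside the sampling error. The reason to act is that the loss is avoidable and concerns the survival data the study was commissioned to collect.

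**What to change.** Reconcile Protocol 8.1, 8.2.2, 8.2.4, 8.3.5, 8.7 and 9.2 with SAP 6.1.3 and 6.1.4, and bring the abstract and SAP 2.1 into line. Define three separate statuses:

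- (a) stopping treatment;
- (b) withdrawal from the study by the investigator or sponsor;
- (c) the patient's withdrawal of consent for further data.

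Then state that:

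1. (a) and (b) do not end safety and vital-status follow-up;
2. deaths and last-known-alive dates collected after (b) are used for OS and 5-year survival;
3. follow-up ends only at death, withdrawal of consent for data, loss to follow-up or study closure.

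The behavioural and administrative grounds need not be deleted, because vital status is then still collected. The change concerns data collection and analysis only and alters no treatment rule. It costs amendment wording in both documents and continued vital-status contact for a few patients who have already consented.
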